## Study Overview

### A. Study Design

**Design Overview:** We will conduct a 2-group cluster randomized trial comparing eMPI to enhanced usual care (eUC) in 22 Bronx practices serving over 10,000 children with asthma. The randomization will be at the practice level to avoid contamination. Each practice will be matched into 11 similar pairs based on size and type and then randomly assigned to either eMPI or eUC.

Provider adoption of guidelines and utilization of care in all patients (~5,000) ages 2-12 years with persistent or uncontrolled asthma from eMPI and eUC practices will be evaluated using EHR data and practice-based screening for asthma severity and control. We will also enroll a random subset of 512

caregivers of children with persistent/uncontrolled asthma from both study arms to systematically evaluate caregiver-reported child morbidity outcomes and obtain measures not available in EHR. These children will be enrolled at the time of the office visit and followed prospectively for 4 time points - 3, 6, 9, and 12 months after the initial visit - to assess clinical and process-focused outcomes.

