**(1) Physician-diagnosed asthma (based on EHR).**

**(2) Persistent or uncontrolled asthma as per clinic assessment.** Based on NHLBI guidelines, any one of the following: in past month, > 2 days/week with asthma symptoms, >2 days/week with rescue medication use, >2 days/month with nighttime symptoms, or ≥ 2 episodes in the past year that required systemic corticosteroids.

1) Mild persistent or more severe asthma severity, or poor asthma control (see definitions below). \*A different assessment of eligibility will be performed depending on whether or not the child has a current prescription for preventive asthma medication at baseline and parent reports its use. This is consistent with the EPR recommendations that make a strong distinction between classifying asthma severity (for children not using preventive medications) and assessing control (for children using preventive medications). If a child has used a preventive medication in the past, but reports no use of the medication in the prior 3 months, we will assess severity. This 3-month time frame is consistent with the length of "wash-out" time for inhaled steroids.

a) **Children not using a preventive medication at baseline:** Mild persistent to severe persistent asthma. Any 1 of the following, during the prior 4 weeks (as defined by parent interview in the waiting room and EMR review):

- i) An average of >2 days per week with asthma symptoms
- ii) >2 days per week with rescue medication use
- iii) ≥3 nights per month awakened with nighttime symptoms
- iv) Minor limitation of activity
- v) >2 episodes of asthma during the past year that have required systemic corticosteroids

b) **Children using a preventive medication at baseline:** Poor asthma control. Any 1 of the following, during the prior 4 weeks (as defined by parent interview in the waiting room):

- i) An average of >2 days per week with asthma symptoms
- ii) >2 days per week with rescue medication use
- iii) ≥2 nights per month awakened with nighttime symptoms
- iv) Some limitation of activity
- v) >2 episodes of asthma during the past year that have required systemic corticosteroids.

**(3)** Age 2 and 12 years, inclusive.

Additional inclusion criteria will apply to a subset of 512 of children whose caregivers will be interviewed to systematically evaluate experiences with the program and caregiver-reported morbidity outcomes:

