***Exclusion Criteria:***

- (1) The child has other significant medical conditions, such as congenital heart disease, cystic fibrosis, or other chronic lung disease, that could interfere with the assessment of asthma-related measures.

Additional exclusion criteria will apply to a subset of 512 children/caregivers as described above:

- (1) No access to a telephone to conduct follow-up surveys.
- (2) Children in foster care or other situations in which consent cannot be obtained from a guardian.

*Based on our previous studies, we anticipate <10% of children will be excluded based on these criteria.*

**Screening:** In 22 practices, clinic staff (RN/LPN) will ask caregivers of all children 2-12 years of age with asthma to complete a screening survey in EPIC Electronic Health Record (EHR) during the triage portion of their doctor visit. The screening survey questions follow national guidelines and will identify children with persistent or uncontrolled asthma (Appendix A).

**Procedures for enrollment of a subset (n=512):** Clinic staff will inform research team on days of recruitment to obtain consent and baseline assessment from a subset of children with persistent or uncontrolled asthma and their caregivers from whom additional morbidity measures (not present in the EHR) will be collected.

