**eMPI Intervention:** The eMPI components are described in Table 4 and closely mirror implementation strategies recommended by the panel of experts in implementation science for development of a tailored multilevel strategy for implementation. First, at every office visit, caregivers of children ages 2-12 years with persistent or uncontrolled asthma will be asked to complete a screening survey in EPIC Electronic Health Record (EHR) during the triage portion of their doctor visit (Appendix A). Clinic staff will review the answers with the caregiver and read the questions aloud as needed. Based on these responses, a prompt for both the provider and caregiver will be generated in EPIC EHR using a simple algorithm (Appendix B). The *provider prompt* will be delivered to the provider at each visit via EHR and include information on child's current level of asthma severity or control, controller

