will also serve on our *Practice Advisory Board*. The Board will consist of ≥ 2 physicians, 1-2 nurses, 1-2 front desk and administrative staff. The Board will meet monthly during the initiation and consolidation phases to review the study protocol as it relates to the practices, discuss any provider-reported barriers to implementation and identify solutions to address these barriers using a collaborative problem solving approach. These Boards will capitalize on already existing and engaged groups created by the Bronx Ongoing Pediatric Screening in the Medical Home (BOPS) program described in the Preliminary Studies section. To initiate the planning process, we will ask Board members to complete the RE-AIM planning tool to highlight any concerns or barriers to implementation. We will engage providers in a practice improvement process by having the clinic champion discuss feedback received from individual providers and solutions at the regular clinic meetings. We will provide the champion with a tool, updated monthly, to record identified barriers to guideline implementation and ways to address them. We will also collect baseline information on provider corrective actions in EHR; assess provider self-efficacy, provider-caregiver communication, and provider competencies in guideline-based care using a validated survey (Appendix A). During month 1 of the initiation phase, we will provide *practice-level support* (e.g., pocket cards with guidelines, brief interactive seminars, local asthma resources; Appendix C) to the practices to assist providers in implementing the asthma management outlined in the NHLBI guidelines and to help remove practice and provider-level barriers to guideline implementation. The interactive seminars, developed using principles of physician behavior change and led by the PI ([name]) and co-Is ([name], pulmonologist and [name], allergist), will generate enthusiasm around prompting and empower providers to implement desired changes. The seminars will include an overview of guideline-based asthma care and orientation to the prompts, resource guides and the feedback charts. At the end of the seminar, a brief needs assessment survey will be done, and additional resources will be provided based on the needs of the individual practices. Providers will receive continuing education credit for their participation. These sessions will be coordinated by each practice's champion. We will also provide *practice-level feedback*. eMPI practices will receive monthly feedback during the initiation phase on the proportion of visits with appropriate guideline-based preventive actions, and the proportion of patients meeting goals of therapy (limited symptoms, no ED visits/hospitalizations). The feedback will be delivered to the champion who will then share it with the rest of the providers. The information will be presented graphically with other intervention practices displayed by a code for comparison. A Quality Control Tool will be used to measure and assess nurse adoption of the asthma severity/control screening. Research staff will observe nursing staff at least once during the

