#### **Clinic-Level Variables**

The **primary outcome** is a clinic-level variable measured by the proportion of visits with  $\geq 1$  guideline-based corrective actions. To calculate this proportion, the denominator will include only the visits by patients aged 2-12 years with persistent or uncontrolled asthma at the time of visit. We will obtain these data from the EHR at baseline, monthly during the initiation phase (to provide feedback to eMPI practices) and every 3 months thereafter for 24 months. Corrective actions include: (1) prescription of a new preventive asthma medication; (2) increase in dose of a preventive medication (for children already on preventive medication); (3) evaluation and counseling regarding triggers; (4) treatment of co-morbid conditions (e.g., sinusitis, allergic rhinitis, obesity); (5) referral to an allergy or pulmonary specialist. We will consider children receiving any of these guideline-based preventive care measures during the visit as having a corrective action (as not all actions may be necessary for each patient), and also will consider each component of preventive care separately. We collected prospective data on most items included in the corrective action definition in our prior work. Additional corrective actions include recommendations for a follow-up visit specifically to discuss asthma, referrals made to OW, and provision of an asthma action plan or school medication administration form.

**Covariate:** Practice characteristics will include practice size (small, medium, large), practice type (hospital-based practice, Federally Qualified Health Center, neighborhood health center), and patient mix (pediatrics, adult/pediatrics), involvement of support staff in the delivery of preventive asthma care, practice-level changes (e.g., new asthma-related initiatives in the practice). We will obtain this information from the existing database of practices and from interviews with the physician champion and office administrator at each practice.

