### **Summary of Analytic Plan:**

We will use graphical and numerical summaries to describe the outcomes at each assessment point. If distributional assumptions for particular statistical procedures are violated, appropriate transformations will be made or non-parametric tests will be used. All primary and secondary analyses will follow the intent-to-treat principle; all participants will be analyzed in the group to which their clinic was assigned irrespective of their post-randomization behavior, and all participants will be analyzed using multiple imputation techniques. Hypothesis-driven comparisons will be made with control of the type I error rate at 0.05 (two-sided).

**Preliminary Analysis.** We will examine data for out of range values. Descriptive statistics will be generated regarding practice characteristics such as size (small, medium, large), practice type (hospital-based practice, Federally Qualified Health Center, neighborhood health center), and patient mix (pediatrics, adult/pediatrics) to help to understand the sample as well as the generalizability of study findings. We will determine whether there are differences at baseline between the eMPI and eUC providers and patients in demographics and background characteristics. This will include analogs of t-tests (or Wilcoxon rank sum tests) for continuous variables and chi-square (or Fisher's Exact) tests for categorical variables adjusted by generalized estimating equation (GEE) methods for the clustering induced by providers within clinics.

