**Aim 3. To evaluate the process of program implementation:** In order to evaluate the potential for dissemination of this primary care intervention, we will report specific summary measures recommended by the RE-AIM framework. We will compare the provider-level proportion of visits with corrective actions taken by the eMPI providers to that of eUC providers using the same analytic approach stated in Aim 2 (Reach). We will evaluate the impact of eMPI on guideline-based corrective actions and symptoms (*Effectiveness*). We will qualitatively describe problem solving progress that occurs in each practice as part of process of improvement, by coding the specific barriers that arise during implementation and are collected by clinic champions, and the solutions that eMPI practices identify (*Adoption*). We will report consistency with which participants in the intervention arm receive the protocol through EHR data, practice observations of the process of implementation and data collected from OW contacts with participants. Additional measures of implementation of eMPI include 1) caregivers' completion of severity/control assessments at the visit; 2) provider and caregiver receipt of prompts; 3) providers' documentation of asthma discussion (*Implementation*). We will use provider survey responses to evaluate the extent to which each intervention component was continued or modified post-study and sustained effects on the primary outcome (*Maintenance*). Using EHR records of 5,000 children across all four waves of translation, we will determine if eMPI practices will (a) reach successively higher levels of guideline-based care, (b) achieve that level more quickly, and (c) sustain use of guidelines for 18 months. The analytic approach to address this will involve a statistical model with the main effect of intervention condition, time (which represents the level of Implementation), and the indicators of waves (which will allow us to evaluate sustainability), plus all the two-way and three-way interactions. We expect to see specific three-way interaction effects involving trends in rates of guideline-based care over 24 months, with an ever steeper linear increases and less pronounced downturns seen from wave to wave, in eMPI practices vs. eUC. Guideline-based care is intended to ensure that children receive needed services in a more timely fashion. We will examine patterns of utilization by children in both groups using the EHR, including adherence to clinic visits, specialty referrals, emergency and in-patient care, and OW referrals.

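### Entry to the primary denominator depends on a post-randomisation triage screen that also fires the eMPI prompt, so the primary contrast is open to selection bias of uncertain direction

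*Combined protocol and SAP*

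**What the plan says.** Clinic-Level Variables defines the primary proportion and states that "the denominator will include only the visits by patients aged 2-12 years with persistent or uncontrolled asthma at the time of visit". The Aim 1 analysis text repeats the definition.

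Status is set by the clinic. Inclusion criterion (2) reads "Persistent or uncontrolled asthma as per clinic assessment". The Screening paragraph has nursing staff give a survey in the EHR at triage in all practices, and says: "The screening survey questions follow national guidelines and will identify children with persistent or uncontrolled asthma". Study Design says that guideline adoption in all eligible patients "will be evaluated using EHR data and practice-based screening for asthma severity and control".

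In eMPI clinics the survey has a second job. The eMPI Intervention paragraph says: "Based on these responses, a prompt for both the provider and caregiver will be generated in EPIC EHR using a simple algorithm".

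The plan foresees incomplete screening. Aim 3 lists caregivers' "completion of severity/control assessments at the visit" and receipt of prompts as implementation measures. The section on the translational process within eMPI clinics adds: "A Quality Control Tool will be used to measure and assess nurse adoption of the asthma severity/control screening". It also provides for observation of nurses and feedback to them. The eUC paragraph says that children are assessed for severity and control at each visit, but describes no comparable support.

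The Summary of Analytic Plan states: "All primary and secondary analyses will follow the intent-to-treat principle". Multiple imputation is described there for participants and, under Aim 2, for individuals who refuse to continue. No text says how a visit without a completed screen is counted.

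**The concern.** Two events hang on one step that happens after randomisation. If staff skip the survey at an eMPI visit, no prompt is generated, and the visit also has no recorded status with which to enter the denominator. The visits at which the prompt failed are then the visits that go uncounted.

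This bears on the trial's question. The Background says that translation means delivery by clinic staff rather than research staff, at every visit. An eMPI clinic that screened few children could still show a high primary proportion. That could happen in particular during the 18-month sustainability phase, when regular support ends. Aim 3's conclusions on maintenance use the same measure.

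There is a second route to bias. Support for screening is described only for eMPI clinics, so the arms may differ in how many visits they screen and in which ones. The two denominators would then hold different mixes of visits.

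**Working it through.** **1. Can status be known without the survey?** Most criteria under inclusion criterion (2) are recent caregiver reports: symptom days, rescue use, night waking and activity limits. For children on preventive medication, the only source named is the parent interview in the waiting room. For children not on it, EMR review is also named, and steroid courses in the past year may be on record. Without a survey, current status is therefore largely unknown, though not always.

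**2. The plan's own figure.** The Aim 1 power analysis assumes a 25-point difference, an SD of paired differences of 0.20, 11 pairs and 10 df. The non-centrality is (0.25/0.20) × √11 = 4.15, and noncentral-t power at two-sided 0.05 is 96.1%. This agrees with the stated figure of more than 95%. I take 25 points as the difference among screened visits.

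**3. Screened visits against all eligible visits.** The documents do not give these inputs, so they are assumptions:
- s: the share of eligible eMPI visits that are screened
- r: the share of the eMPI effect kept at unscreened eMPI visits
- q: the eUC action rate, taken as equal at screened and unscreened visits

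The eMPI rate over all eligible visits is s(q + 0.25) + (1 − s)(q + 0.25r). Subtracting q gives

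D = 0.25 × [s + (1 − s)r].

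| Completion s | r = 0 | r = 0.5 | r = 1 |
|---|---|---|---|
| 100% | 25 | 25 | 25 |
| 90% | 22.5 | 23.75 | 25 |
| 80% | 20 | 22.5 | 25 |
| 60% | 15 | 20 | 25 |

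Entries are percentage points. The screened-only 25 exceeds the all-eligible figure by a factor of 1.11, 1.25 or 1.67 in the r = 0 column (for example 25/15 = 1.67), and by 1.05, 1.11 or 1.25 in the r = 0.5 column.

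**4. Can the sign reverse?** Suppose half of eligible visits are asthma-focused with a base action rate of 0.60, half are not with a base rate of 0.20, and eMPI adds 0.25 at screened visits only.

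- *Same screening in both arms (90% of focused visits, 50% of others).* Screened-only eMPI: (0.45 × 0.85 + 0.25 × 0.45)/0.70 = 0.707. Screened-only eUC: (0.45 × 0.60 + 0.25 × 0.20)/0.70 = 0.457. The difference is 0.250. Over all eligible visits it is 0.575 − 0.400 = 0.175. The screened-only figure is too large.
- *More selective screening in eUC (eMPI 90%/80%, eUC 90%/40%).* Screened-only eMPI: (0.45 × 0.85 + 0.40 × 0.45)/0.85 = 0.662. Screened-only eUC: (0.45 × 0.60 + 0.20 × 0.20)/0.65 = 0.477. The difference is 0.185. Over all eligible visits it is 0.6125 − 0.400 = 0.213. The screened-only figure is too small.

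**The case against.** A reader might infer that the plan restricts the denominator to screened visits, that this makes the analysis per-protocol, and that the effect is therefore overstated. The documents do not carry that chain.

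- **The restriction is not written.** The denominator is defined by the child's status at the visit, and EMR review is one named source for some children. What is shown is a missing rule for unscreened visits. Exclusion is the plain reading, not stated text.
- **An unscreened eMPI visit is not an untreated one.** It misses the prompts. Seminars, pocket cards, the clinic champion, the advisory board and performance feedback still reach the provider. Analysis by assigned clinic is also kept, so calling this a per-protocol set goes too far.
- **The direction is not fixed.** The same screen filters eUC visits. Stronger screening support in eMPI could leave eUC screening fewer visits, mostly the asthma-focused ones, which is the reversal case above.
- **Poor screening is not hidden from the trial.** Aim 3 reports assessment completion and prompt receipt.

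All four points stand. They limit the claim about direction and size. They do not remove the dependence of the primary denominator on a post-randomisation step, and reporting completion under Aim 3 does not correct the primary result.

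**Conclusion.** The concern holds as an exposure to selection bias, not as a demonstrated overstatement. Visit-level eligibility rests in practice on a screen done after randomisation, that screen delivers the eMPI prompt, and no rule covers visits without it. The primary contrast is therefore not a clean intent-to-treat comparison over all eligible visits.

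The likely direction is upward if completeness and selectivity of screening are similar in the two arms, and it can be downward if eUC is the more selective. Over the completion rates of 60% to 90% shown above, the overstatement is 2.5 to 10 points of 25 with no carry-over and 1.25 to 5 points with half carried over. It is nil with full carry-over or full screening. These figures rest on assumed screening rates and on equal eUC action at screened and unscreened visits. This should be fixed and is cheap to fix, but it does not require a new primary denominator.

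**What to change.** Keep the current primary denominator and add the following before analysis:

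1. State how a visit without a completed screen is handled.
2. Prespecify a key sensitivity analysis with the same matched-pairs permutation test and the same time window. In both arms its denominator is all visits by 2-12-year-olds with EHR-diagnosed asthma. Outcomes Assessment already plans EHR review for all patients with asthma in both arms, and Table 1 already counts such visits.
3. Report screening completion by arm and quarter beside the primary result.
4. Limit the primary conclusion to screened visits if the two analyses disagree or completion differs by arm. Say in advance what counts as disagreement, because some shrinkage is expected.
5. Treat any imputation of status as supportive only. Use fields recorded before the visit, not prescriptions written at it, since a new preventive prescription is itself a corrective action. Check the data needed against the consent waiver, which describes de-identified data obtained at clinic level.

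The cost is some analysis-plan text and clinic-level counts from the same EHR. There are two drawbacks. First, the all-visit effect is diluted by children who need no action. The plan estimates that about half of children with asthma are eligible, so if half of visits are too and eMPI does nothing at the rest, 22.5 points becomes 0.5 × 22.5 = 11.25. Second, providers tick off discussed items on the prompt, so actions may be recorded less fully at unprompted visits.
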